NCT04349371

Title: Chloroquine (CQ) prophylaxis for Health Care Workers at risk for COVID

Short title: Saved by CQ

Clinical Phase: II

PI: [name] MPH

Co-investigator: [name] MPH

Protocol Version: 3.0 (IRB approved 11/09/2020)

**Primary Objective:** The primary objective is to determine the clinical efficacy of CQ in health care workers with moderate to high risk of exposure to COVID-19 in preventing symptomatic COVID-19 infections.

**Secondary Objectives:** Secondary endpoints will explore the efficacy of CQ in preventing any infection as defined by seroconversion to positive anti-COVID antibody status.

**Study Design:** Double blind, placebo controlled, randomized study of CQ in health care workers with risk of COVID exposure. The primary objective is to determine the clinical efficacy of CQ in health care workers with moderate to high risk of exposure to COVID-19 in preventing symptomatic COVID-19 infections. Safety assessments include AEs, vital signs, ECGs, and physical examinations.

Stratification will be based and levels of exposure: -moderate risk: defined by patient facing work in outpatient/in-house clinic at least 2 days/week -high risk: ICU/ER/procedure rooms with aerosolized particles and high risk of contamination Stratification based on age: -Under 50 years of age -Older than 50 years of age

**Sample size:** 175 patients/group. Sample size based on a projection that 15% of healthcare workers will develop symptomatic COVID-19 illness and an anticipated 67% reduction in rate (i.e. 5%) among those treated with CQ. 175 patients per group, allowing for a 10% dropout rate, will permit detection of a difference of this magnitude or greater for the primary endpoint, assuming a two-tailed alpha and 80% power. The trial is not powered on any secondary outcomes or interim analyses.

**Study Duration:** -1 month accrual of patients with treatment duration of 2-3 months or until exposure levels become negligible - 2 month follow up visit, 3 month follow up visit

**Treatment Description:** 3 Patients will receive CQ 500 mg every day for one week, then 500 mg weekly for the duration of the exposure. A dose of 250 mg daily will be allowed for severe GI intolerance.

**Primary Endpoint:** Decrease by 67% in number of symptomatic illness in at risk healthcare workers; a decrease in symptomatic COVID infections from 15% to 5% in the treatment arm.

**Co-primary Endpoint:** Decrease by 70% in number of severe illness in at risk healthcare workers.

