### **Statistical analysis**

Summary statistics for outcomes and predictor variables will be calculated, with comparisons made using Student's t-test and Wilcoxon rank-sum test for normally and non-normally distributed continuous variables, respectively. Counts and percentages will be calculated for categorical variables and compared using  $\chi^2$  or Fisher's exact test as appropriate. COVID disease status will be ascertained based on medical records review for severe hospitalized patients, self-reported history of viral illness with serological confirmation of anti-COVID status, and anti-COVID antibody status. The association between CQ and disease will be explored. Efficacy analyses included all the patients who underwent randomization and who received at least one dose of CQ or placebo (modified intention-to-treat population). The primary end point, the percentage of patients with COVID infection at study end, will be compared in the CQ group and in the placebo group with the use of a stratified Cochran–Mantel–Haenszel test, with strata corresponding to the stratification factors (age and exposure levels). To isolate the association between CQ and possible confounders we will define as those variables associated with both the outcome and the independent variable (CQ). Statistical calculations will be performed using STATA version 12. A two-tailed  $\alpha$  of 0.05 was defined as the level of statistical significance for all tests.

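### The primary outcome in the analysis section has no onset rule, so read literally it counts illness from before the first dose and dilutes the effect

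*Combined protocol and SAP*

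**What the plan says.** The Statistical analysis section gives the rule that would be programmed. The outcome is "The primary end point, the percentage of patients with COVID infection at study end", compared between arms with a stratified Cochran–Mantel–Haenszel test. The population is stated as "Efficacy analyses included all the patients who underwent randomization and who received at least one dose of CQ or placebo". Disease status is drawn from medical records for severe hospitalised cases, from "self-reported history of viral illness with serological confirmation of anti-COVID status", and from antibody status. None of these sources is tied to a date.

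The synopsis describes something narrower. The Primary Objective concerns "exposure to COVID-19 in preventing symptomatic COVID-19 infections", the Primary Endpoint is "Decrease by 67% in number of symptomatic illness in at risk healthcare workers", and the Sample size entry reads "Sample size based on a projection that 15% of healthcare workers will develop symptomatic COVID-19 illness". All three point to new, symptomatic cases.

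The Exclusion Criteria contain no item on earlier COVID-19 or antibody status. The only screening test described in detail is the ECG, and no section schedules a baseline antibody or PCR test. The Secondary Objectives refer to the "efficacy of CQ in preventing any infection as defined by seroconversion to positive anti-COVID antibody status". Seroconversion implies a negative baseline result, but the plan does not say how such a result would enter the primary analysis.

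**The concern.** Status at study end is not the same as an event during follow-up. A worker who was ill before enrolment, still has antibodies and reports the illness meets the definition in the Statistical analysis section on the day of the first dose. Prophylaxis cannot prevent that illness.

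Randomisation spreads such cases equally over the arms in expectation. They add the same amount to both event rates, so the relative reduction shrinks and the comparison becomes noisier. A real effect would look smaller than it is and would be missed more often. If the question is left until the data are in, someone will have to decide which illnesses are old, and without onset dates that cannot be done reliably.

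**Working it through.** **Inputs from the documents.** 15% vs 5%, 80% power and 175 per group including 10% dropout (Sample size); two-sided alpha of 0.05 (Statistical analysis); 1:1 allocation (the randomisation text under the ECG heading).

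**The planned size first.** The normal-approximation formula is n = [1.960·√(2p̄(1−p̄)) + 0.842·√(p1(1−p1) + p2(1−p2))]² / (p1−p2)².

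- With p̄ = 0.10: (1.960·√0.18 + 0.842·√0.175)² / 0.01 gives 141 per arm, or 141/0.9 = 157 with dropout. This does not match 175.
- With continuity correction: 160 per arm, which becomes 160/0.9 = 178 or 160 × 1.1 = 176. This is close to 175.

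The plan does not say which version was used, so both are shown below. The evaluable number is 175 × 0.9 = 157.5, taken as 157 per arm.

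**Assumed, not in the documents.** s is the share of each arm with COVID-19 before the first dose (2–20%). v is the fraction of those who would be counted because they report a past illness (a quarter or a half). Participants with prior infection are assumed to have no new event. Everyone else has 15% vs 5%.

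**Event rates.**

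- Prior illness counted: p1 = s·v + (1−s)·0.15 and p2 = s·v + (1−s)·0.05.
- Onset rule applied, same 157 per arm: p1 = (1−s)·0.15 and p2 = (1−s)·0.05.

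**Power.** Exact binomial power of the unstratified chi-square test, as an approximation to the planned stratified test. Each cell shows uncorrected / continuity-corrected power. With s = 0 it is 0.861 / 0.807.

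| s | counted, v = ¼ | counted, v = ½ | onset rule |
|---|---|---|---|
| 2% | 0.836 / 0.777 | 0.819 / 0.757 | 0.853 / 0.797 |
| 5% | 0.795 / 0.729 | 0.751 / 0.686 | 0.840 / 0.781 |
| 10% | 0.721 / 0.649 | 0.638 / 0.577 | 0.817 / 0.753 |
| 20% | 0.565 / 0.496 | 0.455 / 0.399 | 0.761 / 0.691 |

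The loss caused by the counting rule is the gap between a counted column and the last column. The fall from the s = 0 row to the last column is depletion: fewer people can have a new event, and no counting rule recovers that.

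**Worked example, s = 10%, v = ½.** p1 = 0.05 + 0.135 = 0.185 and p2 = 0.05 + 0.045 = 0.095. The reduction is 1 − 0.095/0.185 = 49% instead of 67%. About 157 × 0.05 = 7.9 old cases per arm would be counted: 0.05/0.185 = 27% of placebo events and 0.05/0.095 = 53% of CQ events.

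**Type I error.** With no drug effect the rejection rate is 0.049 (corrected 0.034) at 15% in both arms, and 0.050 (corrected 0.035) at 18.5% in both arms. It is not inflated.

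**Restricting to baseline antibody-negatives instead.** At s = 10%, n = 157 × 0.9 ≈ 141 per arm at 15% vs 5% gives 0.817 / 0.765, against 0.817 / 0.753 for the onset rule in all dosed participants. The difference is small.

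**The case against.** The strongest reply is that this is a silence, not a rule. The synopsis speaks of new cases throughout. The Study Stopping Rules make a symptomatic COVID-19 infection a trigger for an enrolment hold, which makes sense only for on-study events. A history of illness could also mean history over the study period. An analyst reading the whole document might well count new events only. It stands that the plan nowhere says that old infections are to be included, and a reader should not infer that it does. But the intended meaning has to be brought in from other sections, and without a required onset date it cannot be applied dependably to self-reported illness.

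A second reply is that limiting the endpoint to symptomatic illness solves the problem. It removes asymptomatic prior seropositives, but a past illness confirmed by persisting antibodies is symptomatic and still qualifies.

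A third reply is that every input driving the loss is assumed. That stands in full. The 15% may also already average over workers with earlier infection, in which case multiplying it by (1−s) counts depletion twice.

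**Conclusion.** The gap is real and should be fixed. The Statistical analysis section states a status-at-study-end rule that does not implement the incident, symptomatic objective. Read literally, it biases the estimated effect towards zero.

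The size depends on assumptions about s and v. Comparing counting with not counting, uncorrected power is 0.84 vs 0.85 at a 2% share with a quarter counted, 0.75 vs 0.84 at 5% with half counted, and 0.64 vs 0.82 at 10% with half counted. The continuity-corrected pairs are 0.78 vs 0.80, 0.69 vs 0.78 and 0.58 vs 0.75. At the low end the loss is under 2 points (0.853 − 0.836 = 0.017).

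Three stronger readings are not supported:

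- That power falls from 0.86 to 0.64 because of the counting rule. At a 10% share part of that fall is depletion; the avoidable part is 0.82 to 0.64.
- That the trial could produce a false positive this way. Balanced old cases leave type I error unchanged.
- That a specific loss follows if antibody status alone makes a case. Asymptomatic new infections would then count too, 15% vs 5% would no longer be the base, and the documents give no rates for that endpoint.

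**What to change.** Settle the following before unblinding.

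1. Reconcile the primary endpoint in the Statistical analysis section (COVID infection) with the synopsis (symptomatic COVID-19). Count as primary events only confirmed symptomatic illness with onset after the first dose, and record the onset date of every self-reported illness.
2. Keep the all-dosed population for the primary analysis under this onset rule. Where a baseline antibody result or stored sample exists, define seroconversion among baseline-negatives and pre-specify a supporting analysis of the primary endpoint in that group.
3. State two limitations. Infections incubating at the first dose would still count. Without a baseline result, old antibodies could confirm a later illness that was not COVID-19.

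The cost is revised wording, one data item and slightly fewer counted events; no new blood draw is needed. The rule does not guarantee 80% power: with the onset rule at a 10% share it is 0.82 uncorrected but 0.75 continuity-corrected.

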### **Rationale:**

We generally consider hydroxychloroquine and chloroquine as being effective in lupus, in part due to inhibition of type I interferon (considered our innate first line defense antiviral response), which has often raised concern about susceptibility to viral infection. However, data are accumulating at a very rapid rate that there may be a paradox. By raising endosomal pH (one of the mechanisms that leads to decreased TLR ligation and decreased IFN) COVID viral replication itself is decreased. Since acidification is crucial for endosome maturation and function, Liu and colleagues suggest that endosome maturation could be blocked at intermediate stages of endocytosis, which would then result in decreased transport of virions to the ultimate releasing site. A study by Goa et al. suggests that chloroquine has efficacy against the associated pneumonia in multicenter clinical trials conducted in China. Additionally, there have been two other small trials that raise more questions than provide definitive answers to the question of hydroxychloroquine efficacy in COVID-19. Specifically, the study by Gautret et al. was a single arm protocol in which 20 confirmed COVID-19 patients were given 600mg of hydroxychloroquine daily (and in some cases azithromycin) and their viral load in nasopharyngeal swabs was tested. Six patients were asymptomatic, 22 had upper respiratory tract infection symptoms and eight had lower respiratory tract infection symptoms. A significant reduction of viral carriage was reported. Of note, levels of HCQ were in accord or lower than those seen in our lupus patients prescribed 5mg/kg. The heterogeneity of the patients included, selection of the control population, high rate of lost to follow-up and handling of missing

observations raise concerns about their conclusions. The other trial is a 30 patient, placebo-controlled study of hydroxychloroquine in patients with relatively mild COVID-19 infections, using 400 mg of HCQ daily, did not show any differences between drug and placebo groups in viral clearance, duration of hospitalization, and radiological progression of COVID-19 pneumonia. CQ and HCQ have been used interchangeably in the treatment and prophylaxis of malaria as well as the treatment of SLE. The current study proposes to evaluate the efficacy of CQ in preventing COVID-19 infections.
